6.4 Administration Rate

Prior clinical trials have used rates up to 30×10^6 hMSC/min where no infusion related toxicity was observed.

In the proposed study, the cell dose to be delivered is 100 million (100×10^6) MSC/infusion, reconstituted as 2 million MSC/mL, in the following total volume:

100 million dose (2.5 million MSC/min) and Placebo will be prepared in an 80ml bag

Investigational product is placed in an 80ml bag and will be delivered at a rate of 2mL/min, and delivered at a maximum rate of 2.5×10^6 MSC/minute, which will last approximately 40 minutes to complete.

The infusion bag will be flushed with an additional 25 ml of 0.9% normal saline at the completion of allo-MSD infusion and delivered at a rate of 2ml/min.

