| STUDY OBJECTIVES | 
Test the hypothesis that intravenous (IV) delivery of MSCs improves coronary artery endothelial function (assessed by fractional flow reserve (FFR) and coronary flow reserve (CFR) at 6 months), systemic endothelial function (assessed by FMD and EPC-colony assay), and angina symptoms (assessed by Seattle Angina Questionnaire) in type 2 diabetic patients with symptomatic IHD compared to placebo.
 
Test the hypothesis that allogeneic MSCs promote systemic and coronary endothelial repair through rescue of bone marrow progenitors in type 2 diabetic patients with symptomatic IHD compared to placebo.
 |
| STUDY DESIGN | Randomized, Double Blind, Placebo controlled, Pilot Trial |
| INVESTIGATIONAL PLAN | 
30 type 2 diabetic patients with symptomatic IHD that undergo standard-of-care coronary angiography with or without Percutaneous Coronary Intervention (PCI) and meet all the inclusion and none of the exclusion criteria will be randomized to receive, within 2 weeks post- standard-of-care coronary angiography , either allogeneic MSCs or placebo in a 1:1 blinded fashion:
 
Group A (15 subjects): Allogeneic MSCs Fifteen (15) subjects will be treated with a single administration of intravenous allogeneic hMSCs (100 million).
 
Group B (15 subjects): Placebo (Cell-free PlasmaLyte-A medium supplemented with 1% HSA) Fifteen (15) subjects will be treated with intravenous placebo infusion.
 
 - Patients will be followed for scheduled outcome and safety assessments at 1, 3 and/or 6 months and 12 months post-infusion. - A bone marrow biopsy will be obtained from participants in a sub-study at the 3-month follow up for cellular and molecular studies (separate informed consent document). |
| ROUTE OF ADMINISTRATION | Peripheral Intravenous Infusion |
| DURATION OF STUDY PARTICIPATION | 12 months |
| SUBJECT POPULATION | 30 subjects age >18 with type 2 diabetes and symptomatic IHD with an indication for standard-of-care coronary angiography with or without PCI |

| | |
|-------------------------|---|

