6.3 Dosage Rationale

A safety profile for IV infusion of MSCs was based on outcomes from previous completed toxicology results[10, 49]. The results from these previous studies demonstrate that the product can be administered intravenously without toxic events at up to 65×10^6 MSC/kg dose delivered in one bolus infusion or at 100×10^6 MSC/kg cumulative dose delivered by 5 infusions (20×10^6 MSC/kg per infusion).

The evidence supports the conclusion that it is feasible to dose subjects in this study based on a standard dose of MSCs rather than per kilogram of body weight. The total cell number corresponds to a range of $1.3 - 4.4 \times 10^6$ MSCs per kg per infusion for subjects with 45kg to 150kg body weight.

In addition, the data from the administration of allogeneic MSCs in the DCM (IND #: 14419; NCT01087996) trial supports the clinical safety of the proposed MSC doses to be administered. Therefore, results from previous trials support the rationale on the safety and potential efficacy of the selected maximum dose of 100×10^6 allogeneic MSCs.

A previous pilot study was conducted to compare the effects of two different doses of MSC given via IV infusion in type 2 diabetic subjects (ACESO). The results of this study showed that both the 20 and 100 million cell doses are safe but the 100 million dose was the optimal dose and was selected to be used for this study (results showed above).

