6.7.2 Investigational Product Accountability Procedures

In accordance with all applicable regulatory requirements, the Cell Processing Laboratory will maintain a record of the investigational products hMSCs received, dispensed, administered, destroyed, or returned. The final disposition of all unused, empty, and partially used Cryocyte™ bags will be handled in accordance with the drug preparation manual.

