APPENDIX 1: Infusion Guidelines

Prior to the start of the infusion the following procedures and assessments will be conducted on the study subject:

1. Vital Signs: Blood pressure, heart rate, respiratory rate, and temperature, will be measured within 15 minutes prior to the initiation of the infusion.
2. Oxygen saturation will be continuously monitored by pulse oximetry for at least 30 minutes prior to initiation of IP infusion.
3. Confirm that IV access is established and that the IV catheter is no smaller than 20 gauge
4. Study personnel needs to verify that the following pre-medications have been administered 30 minutes to an hour prior to infusion, unless otherwise determined by the physician:

- a. Hydrocortisone 25 – 50 mg IV
- b. Diphenhydramine (Benadryl) 25 – 50 mg IV

Note: No other medications should be given during the infusion unless determined medically necessary by the Investigator.

5. Document pre-medications given prior to infusion on the source documents
6. Required IV Infusion materials as follows:
 - 0.9 % normal saline IV infusion bag
 - IV Pump tubing
 - IV extension tubing (unless using a central line)
 - Volumetric infusion pump
 - Gloves
 - Remove 0.9% normal saline infusion bag and connect IV tubing to the volumetric infusion pump
 - Cover the IV tubing with the blinding material provided with the infusion bag by the drug preparation technician.

During the IP infusion the following procedures and assessments will be conducted on the study subject:

1. Monitor the subject continuously with pulse oximetry
2. Hang the blinded infusion bag. Investigational product (IP) should not be “piggybacked” through another line
3. Intravenously administer the IP at a rate of 2ml/min.

Note: Study personnel administering the IP must be present throughout the infusion process. The Investigator must be available at the site during the infusion process in case an emergency should arise.

4. Record the start time of the infusion bag
5. Gently squeeze the infusion bag several times every 15 minutes to assure uniform dispersion of contents
6. Vital signs and O₂ saturation will be measured every 15 minutes until the end of IP infusion
7. Record the total volume infused from the IP bag
8. At the end of the IP infusion, close the line and flush 25ml of 0.9% normal saline into the luer lock connector on the bottom of the IP bag, reopen line and allow to infuse at a rate of 2mL/min until completion.

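### Two dose figures are wrong as written: the concentration in Section 6.4 should be 1.25, not 2, million MSC/mL, and the per-kilogram range in Section 6.3 should be 0.67–2.2, not 1.3–4.4, million MSC/kg

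*Combined protocol and SAP*

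**What the plan says.** Section 6.4 (Administration Rate) sets the dose at 100 million MSC per infusion, "reconstituted as 2 million MSC/mL, in the following total volume". The next line reads "100 million dose (2.5 million MSC/min) and Placebo will be prepared in an 80ml bag". The section then gives a delivery rate of 2 mL/min, a maximum of 2.5 million MSC per minute, and a duration "which will last approximately 40 minutes to complete". Appendix 1 repeats the pump rate: "Intravenously administer the IP at a rate of 2ml/min".

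Section 6.3 (Dosage Rationale) defends dosing "based on a standard dose of MSCs rather than per kilogram of body weight". It says the total cell number corresponds to 1.3–4.4 million "MSCs per kg per infusion for subjects with 45kg to 150kg body weight". The same section names 100 million as the selected maximum dose. The Protocol Synopsis describes treatment as a "single administration of intravenous allogeneic hMSCs (100 million" cells), and Section 3.1 gives the same dose.

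**The concern.** Dose, volume, flow rate, cell rate and duration are tied together by simple division, so one wrong entry can be identified. In Section 6.4 the concentration does not fit the others. It is a product figure in a section that governs how the infusion is given. If it is followed at the stated pump rate, the infusion exceeds the maximum cell rate that the same section sets.

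The per-kilogram range in Section 6.3 does not follow from 100 million cells at the stated body weights. It is the only figure there that puts the fixed dose on the same scale as the cited toxicology levels, such as the 65 million MSC/kg single bolus. Anyone reading it for exposure is given a value twice too high.

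**Working it through.** **Inputs.** From Section 6.4: dose 100 million MSC; concentration 2 million MSC/mL; volume 80 mL; flow 2 mL/min (also Appendix 1); maximum 2.5 million MSC/min; about 40 min; earlier trials at up to 30 million/min without infusion toxicity. From Section 6.3: 1.3–4.4 million MSC/kg for 45–150 kg; toxicology bolus 65 million MSC/kg.

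**Section 6.4: figures that reproduce**

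- Duration = volume / flow = 80 / 2 = 40 min. Matches.
- Cell rate = dose / duration = 100 / 40 = 2.5 million/min. Matches.
- Concentration = dose / volume = 100 / 80 = 1.25 million/mL. The protocol says 2, which is 2 / 1.25 = 1.60 times as much.

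**Section 6.4: consequences of 2 million/mL**

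| Reading | Volume | Duration | Cell rate | Cells given |
|---|---|---|---|---|
| Keep 100 million, flow 2 mL/min | 100 / 2 = 50 mL | 50 / 2 = 25 min | 2 × 2 = 4.0 million/min | 100 million |
| Keep a full 80 mL, flow 2 mL/min | 80 mL | 40 min | 4.0 million/min | 80 × 2 = 160 million |
| Keep 100 million and 2.5 million/min | 50 mL | 50 / 1.25 = 40 min | 2.5 million/min | 100 million, but flow falls to 2.5 / 2 = 1.25 mL/min |

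The first two rows exceed the stated maximum by 4.0 / 2.5 = 1.60. The third keeps the maximum only by changing both the volume and the pump rate, the latter in Appendix 1 as well. Counting the 25 mL saline flush does not help: 100 / 105 = 0.95 million/mL and 105 / 2 = 52.5 min.

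Against earlier experience, 4.0 / 30 = 13% of the rate cited without infusion toxicity.

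**Section 6.3: dose per kilogram = dose / weight**

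| Total cells | At 150 kg | At 45 kg |
|---|---|---|
| 100 million (this trial) | 100 / 150 = 0.67 million/kg | 100 / 45 = 2.22 million/kg |
| 200 million | 200 / 150 = 1.33 million/kg | 200 / 45 = 4.44 million/kg |
| Printed | 1.3 million/kg | 4.4 million/kg |

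Working backwards, the printed range needs 1.3 × 150 = 195 to 4.4 × 45 = 198 million cells. For 100 million cells it would fit weights of 100 / 4.4 = 22.7 kg to 100 / 1.3 = 76.9 kg. Reading the weights as pounds gives 1.47–4.90 million/kg, which does not match either.

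Margin to the 65 million/kg bolus at 45 kg: 65 / 2.22 = 29-fold with the correct dose, against 65 / 4.4 = 15-fold as printed.

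**The case against.** The arithmetic is hard to dispute; the case on the other side is about meaning and consequence.

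- *The 2 million/mL might be an intermediate step before dilution into the bag.* The sentence introduces a total volume and the next line names the 80 mL bag. No dilution step is described. If one exists, the protocol needs to say so.
- *The 80 mL might be bag capacity rather than fill.* A 50 mL fill at 2 mL/min would run 25 minutes, contradicting the stated 40.
- *Nobody may prepare product from this sentence.* Manufacture is referred to other documents, designated technicians prepare the infusions, and a preparation manual exists. Section 6.7.2 cites that manual only for disposing of bags, which "will be handled in accordance with the drug preparation manual". It may hold the right concentration, but the protocol would then disagree with it.
- *Exceeding the maximum requires staff to follow the concentration and ignore the figures beside it.* This is fair and limits the practical risk. It is also fair that dose, volume and flow are the three independent inputs, with duration and cell rate following from them.
- *Neither error does harm.* This stands. Dosing is fixed, so nobody doses from the per-kilogram range. Section 6.3 states no safety margin, and the 29-fold and 15-fold figures are derived here. The dose rationale also rests on earlier trials, including the pilot in diabetic subjects. Correcting the range strengthens the safety argument.
- *The equal fill volume is largely implied already.* This is also fair. Stating it is a clarification, with one modest benefit: Appendix 1 has infusion staff record the start time and total volume infused, so a 50 mL active fill against an 80 mL placebo fill could reveal the arm. Nothing shows that this would happen.

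**Conclusion.** Both figures are wrong as written. The concentration is overstated by 60% (2 against 1.25 million MSC/mL) and, at the stated pump rate, conflicts with the protocol's own maximum cell rate. The per-kilogram range is overstated two-fold (1.3–4.4 against 0.67–2.2 million MSC/kg). The concentration matters more, because it describes the product to be infused; the range is supporting rationale.

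The conclusion rests on the 100 million dose, stated consistently across the synopsis and Sections 3.1, 6.3 and 6.4, and on reading 80 mL as the filled volume, which the 40 minutes at 2 mL/min supports. The preparation manual was not available, so 1.25 million/mL is the value the protocol's other figures require and still needs confirming there. The printed range matches 200 million cells, but the documents do not say where it came from. This should be fixed, though it has no effect on patient risk as far as shown, and none on any endpoint, sample size or analysis.

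**What to change.** In Section 6.4, change the concentration to 1.25 million MSC/mL once it has been checked against the drug preparation manual, and state that active and placebo bags are both filled to 80 mL. The 2 mL/min in Section 6.4 and Appendix 1 then stays as it is. In Section 6.3, replace the range with 0.67–2.2 million MSC/kg for 45–150 kg.

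The cost is two corrected numbers, one clarifying phrase and one check against the manual. No extra patients, visits or procedures are needed.

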6.4.1 Infusion Monitoring

Subjects will be monitored in the Clinical Translational Research Site (CTRS) at the University of Miami Hospital (UMH) for two hours prior to infusion to establish baseline vital signs (oxygen saturation, heart rate, blood pressure, respiration rate, and temperature) every 15 minutes. Vital signs will be recorded at the start and at 15-minute intervals throughout the infusion.

Once the infusion is begun, 2L/min oxygen via nasal cannula will be provided if the oxygen saturation drops below 90% on room air. The infusion will be stopped if the oxygen saturation does not return to >93% within 3 minutes of initiating supplemental oxygen or if the subject requires greater than 2L/min supplemental oxygen to achieve the required saturation of >93%. If a subject requires the addition of oxygen, it will be continued for 4 hours after the completion of the infusion. At that time, oxygen will be weaned off to maintain a saturation >93% on room air.

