9.2.1 Pulse Oximetry

Pulse oximetry will be used to observe oxygen saturation when measuring vital signs at the infusion visit (Reference Appendix 1). Pulse oximetry will be monitored throughout infusion and continuously for 2 hours post-infusion. Subjects should have a resting oxygen saturation of $\geq 93\%$ prior to infusion. Subjects requiring oxygen, need the peripheral artery oxygen saturation (SaO_2) to be $\geq 93\%$ when given a maximum of 2L/minute supplemental O_2 via nasal cannula. Infusion toxicity will be assessed based on decreases in oxygen saturation during infusion. The infusion will be stopped if the oxygen saturation does not return to $>93\%$ within 3 minutes of initiating supplemental oxygen or if the subject requires greater than 2L/min supplemental oxygen to achieve the required saturation of $>93\%$. If this occurs, then subjects will be admitted to the hospital for observation.

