9. Discard IV tubing according to established guidelines
10. Return the blinded IP infusion bag to the cell-processing technician.

After the IP infusion the following procedures and assessments will be conducted on the study subject:

1. Vital signs will be monitored at 15 minutes, 30 minutes, 1 hour, and 2 hours post IP infusion
2. The subject will be monitored for a minimum of 2 hours post IP infusion with continuous pulse oximetry
3. If the O₂ saturation decreases to < 93% over a continual period of 3 – 5 minutes then supplemental oxygen may be added or increased during the two hours post-infusion observation period.
4. If at the end of the 2-hour observation period, if a subject's O₂ saturation stays below 93% then the subject will be provided additional oxygen to maintain a saturation of >93% at room air up to 4 hours post infusion.
5. After the minimum two-hour observation period, the subject will be discharged, if no complaints are experienced, such as shortness of breath or other objective signs of cardiorespiratory compromise.
6. Subjects not meeting criteria for discharge will be assessed by the Investigator during the observation period to further determine hospitalization otherwise not specified in the protocol.

Subject Stopping Guidelines:

- Any subject who develops persistent (that is, still existing more than 3 hours after the end of IP infusion) cardiorespiratory signs or symptoms including hypoxemia (defined per oxygenation criteria of 93% on room air at rest, or shortness of breath, tachypnea, tachycardia, hypotension, or palpitations) will continue with all scheduled follow-up if such follow-up is considered safe in the opinion of the Investigator. The infusion will be stopped if the oxygen saturation does not return to >93% within 3 minutes of initiating supplemental oxygen or if the subject requires greater than 2L/min supplemental oxygen to achieve the required saturation of >93%. If a subject requires the addition of oxygen, it will be continued for 4 hours after the completion of the infusion. At that time, oxygen will be weaned off to maintain a saturation >93% on room air.
- Any subject whose infusion is stopped due to cardiorespiratory distress will receive no further IP infusions but will continue with all scheduled follow-up if such follow-up is considered safe in the opinion of the Investigator.

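### The infusion oxygen, discharge and admission instructions disagree at specific points across sections 6.4.1, 9.2.1, 9.2.5 and Appendix 1

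*Combined protocol and SAP*

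**What the plan says.** **Section 6.4.1 (during infusion).** The oxygen trigger is: "2L/min oxygen via nasal cannula will be provided if the oxygen saturation drops below 90% on room air". The stop rule is: "The infusion will be stopped if the oxygen saturation does not return to >93% within 3 minutes of initiating supplemental oxygen", or if more than 2 L/min is needed to exceed 93%. Once oxygen has been added, "it will be continued for 4 hours after the completion of the infusion", after which it is weaned to room air.

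**Section 9.2.1.** "Subjects should have a resting oxygen saturation of" at least 93% before infusion. Subjects who need oxygen must reach at least 93% on no more than 2 L/min. The section repeats the stop rule and then adds: "If this occurs, then subjects will be admitted to the hospital for observation".

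**Section 9.2.5.** This refers the reader to Appendix 1 for observation and discharge after administration.

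**Appendix 1, after infusion.**
- Item 3: if saturation is below 93% for 3 to 5 minutes, "then supplemental oxygen may be added or increased during the two hours post-infusion observation period".
- Item 4: if it is still below 93% at two hours, the subject is "provided additional oxygen to maintain a saturation of >93% at room air up to 4 hours post infusion".
- Item 5: "After the minimum two-hour observation period, the subject will be discharged, if no complaints are experienced". The item gives shortness of breath and objective signs of cardiorespiratory compromise as examples.
- Item 6: subjects who do not meet the discharge criteria are assessed by the Investigator, who decides on any hospitalization that the protocol does not already specify.
- Stopping guidelines: these repeat the stop rule and the 4-hour oxygen rule, but not the admission rule.

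**The concern.** Staff will work from these instructions at the bedside, and the section that governs discharge sends them to Appendix 1. If that sheet lacks a step that another section makes mandatory, or contains one that cannot be carried out, care will depend on which page is open.

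There is also a consequence for the safety data. Inpatient hospitalization is one of the seriousness criteria in section 9.6, so whether a subject is admitted after a desaturation can decide whether the event is recorded as an SAE. Section 9.15 has all AEs documented as unexpected. Section 9.2.4 puts accrual and treatment on temporary hold for unexpected SAEs within 30 days that are reasonably attributable to the product or procedure, and it lists cardiorespiratory distress during infusion among them. The admission wording could therefore bear on whether that guideline is reached.

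**Working it through.** The plan gives no figure to reproduce. The check takes each type of subject and asks whether one course of action satisfies every section.

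1. **Infusion stopped on the oxygen rule; subject recovered and without complaints at two hours.** Section 9.2.1 admits. Appendix 1 item 5 discharges. Item 6 does not settle it, because it reaches only subjects who fail the discharge criteria, and this subject meets them. The two instructions conflict.

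2. **Still below 93% at two hours.** Item 4 gives oxygen and sets its target at room air. A subject receiving oxygen is not at room air, so the item cannot be followed as written. Item 4 also treats 4 hours as a ceiling, while section 6.4.1 and the Appendix 1 stopping guideline treat it as a fixed duration.

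3. **Already on 2 L/min before infusion, saturation exactly 93%.**
   - Entry condition: 93 ≥ 93 on 2 L/min is true, so the infusion may start.
   - Stop condition: 93 > 93 is false, so exceeding 93% would take more than 2 L/min, which is a ground for stopping.
   - The subject meets both. In addition, the section 6.4.1 trigger is a room-air reading, and the 3-minute clock runs from the start of supplemental oxygen. Neither describes someone already on it.

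4. **Given oxygen during infusion, recovered, no complaints at two hours.** Oxygen continues to 4 hours. Item 5 discharges after a minimum of 2 hours and has no criterion on oxygen use. The gap is 4 − 2 = 2 hours. Because two hours is only a minimum, later discharge satisfies both sentences. The relation is ambiguous, not contradictory.

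5. **Below 90% during infusion, or below 93% afterwards.** The two triggers belong to different phases. There is no conflict.

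6. **Room-air subject steady at 93%.** Section 6.4.1 starts oxygen only below 90%, so the stop clock never starts. There is no conflict.

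7. **Stop rule.** It is worded identically in sections 6.4.1 and 9.2.1 and in Appendix 1.

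Scale: with 15 subjects per arm (section 3.1), one event recorded or not recorded as serious is 1/15 = 6.7 percentage points of that arm.

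**The case against.** The best defence is that a reader holding all the sections together can satisfy most of them. Two hours is a minimum, Appendix 1 itself repeats the 4-hour oxygen rule, and item 6 leaves to the Investigator only hospitalization not specified elsewhere, which can be read as deferring to section 9.2.1. The room-air phrase sits next to text on weaning to room air and may be a drafting slip. Section 9.2.1 does not say outright that subjects requiring oxygen needed it before the infusion, and nothing suggests how many, if any, would enrol on oxygen.

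Much of this stands, and it rules out some stronger readings:
- A reader might infer that the 90% and 93% triggers contradict each other. They do not, because one applies during the infusion and the other after it.
- A reader might infer that staff can never comply with every section. That is too broad: the 2-hour and 4-hour rules can both be met.
- A reader might infer that a room-air subject accepted at 93% faces an impossible recovery target. A steady 93% never triggers the rule, and recovery after a fall is read on oxygen.
- A reader might infer that stopped infusions would be counted differently. This is not shown: the stop rule is the same in all three places, and the admission, oxygen-duration and discharge points concern care after the infusion has ended or been stopped.

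The defence does not remove the admission conflict for a subject who meets item 5, the room-air wording in item 4, or the boundary case on 2 L/min.

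**Conclusion.** The concern holds at four specific points. Admission after a stopped infusion is in direct conflict for a recovered subject. The item 4 oxygen instruction cannot be followed as written, and its duration is worded differently from the 4-hour rule elsewhere. The entry and stop conditions overlap at exactly 93% on 2 L/min, and the trigger does not cover subjects already on oxygen. Discharge is ambiguous against the 4-hour oxygen rule, although both can be met.

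The effect is on bedside safety and on whether a desaturation leads to an admission and so to an SAE. No efficacy endpoint, sample size or significance level is involved. The documents do not allow an estimate of how many subjects would be affected. The conclusion assumes that admission for observation counts as inpatient hospitalization under section 9.6. The boundary case further assumes that the section 9.2.1 provision for subjects requiring oxygen applies before infusion, as its position in the paragraph suggests.

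**What to change.** Reconcile sections 6.4.1, 9.2.1 and 9.2.5 and Appendix 1 into one set of infusion instructions held in one place, with the other sections referring to it and not restating it. It should settle:

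- what happens after an infusion is stopped on the oxygen rule, and how that fits with the discharge item;
- the item 4 oxygen wording, and the duration of oxygen against the time of discharge;
- the entry value against the recovery value;
- how the trigger, the stop clock and weaning apply to a subject already on oxygen, or whether such subjects are intended at all.

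The values and rules are for the sponsor's clinicians to decide. The cost is a change of protocol wording and a one-page infusion sheet; no procedure is added.
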